5.1.3 Statistical Methods for Observational Objectives

5.1.3.1 Hypotheses

No hypotheses will be tested. Descriptive statistics will be presented.

5.1.3.2 Statistical Methods

Immunogenicity

Descriptive statistics will be provided for the hSBA antibody titers against meningococcal serogroups contained in MenACYW conjugate vaccine when it is administered alone or concomitantly with MenB vaccine for MenACYW conjugate vaccine-primed subjects and Menveo vaccine-primed subjects. Descriptive statistics will also be provided for the rSBA antibody titers against meningococcal serogroups contained in MenACYW conjugate vaccine when it is administered alone in a subset of 50 subjects per Group 1 and Group 2 (total of 100 subjects). In general, categorical variables will be summarized and presented by frequency counts, percentages, and CIs. The 95% CIs of point estimates will be calculated using the normal approximation for quantitative data and the exact binomial distribution (Clopper-Pearson method) for percentages. For GMTs, 95% CIs of point estimates will be calculated using normal approximation assuming they are log-normally distributed.

Reverse Cumulative Distribution Curve (RCDC) figures will be provided for the antibody titers against meningococcal serogroups contained in MenACYW conjugate vaccine treatment groups for MenACYW conjugate vaccine-primed subjects and Menveo vaccine-primed subjects.

In summary, descriptive analyses on A, C, Y, and W serogroups on D0, D06, and D30 after vaccination with MenACYW conjugate vaccine when it is administered alone or concomitantly with MenB vaccine using hSBA will include but not be limited to:

- 1) GMT and 95% CI
- 2) Titer distribution and RCDC
- 3) Percentage of subjects with titer $\geq 1:4$ and $\geq 1:8$ and 95% CI
- 4) Percentage of subjects with titer ≥ 4 -fold rise from pre-vaccination to post-vaccination, and 95% CI
- 5) Percentage of subjects with hSBA vaccine seroresponse*

*hSBA vaccine seroresponse for serogroups A, C, Y, and W is defined as:

- For a subject with a pre-vaccination titer $< 1:8$, the post-vaccination titer must be $\geq 1:16$
- For a subject with a pre-vaccination titer $\geq 1:8$, the post-vaccination titer must be at least 4-fold greater than the pre-vaccination titer.

Descriptive analyses on A, C, Y, and W serogroups on D0 and D30 after vaccination with MenACYW conjugate vaccine using rSBA will include but not be limited to:

- 1) GMT and 95% CI
- 2) Titer distribution and RCDC
- 3) Percentage of subjects with titer $\geq 1:8$ and $\geq 1:128$ and 95% CI
- 4) Percentage of subjects with titer ≥ 4 -fold rise from pre-vaccination to post-vaccination, and 95% CI
- 5) Percentage of subjects with rSBA vaccine seroresponse*

*rSBA vaccine seroresponse is defined as a post-vaccination titer $\geq 1:32$ for subjects with pre-vaccination rSBA titer $< 1:8$, or a post-vaccination titer ≥ 4 times the pre-vaccination titer for subjects with pre-vaccination rSBA titer $\geq 1:8$.

Data of subjects from MET50 (or MET43, if applicable) and MET59 will be combined and paired to evaluate antibody persistence and overall trends over 3-6 years post-priming with an MCV4 (ie, MenACYW conjugate vaccine-primed subjects or Menveo vaccine-primed subjects). If Menveo vaccine-primed subjects that were not part of MET50 are recruited, those will not contribute to the assessment of antibody persistence.

Safety

Safety results in Section 4.3.2.2 will be described for subjects in all study groups. The main parameters for the safety endpoints will be described by 95% CIs (Clopper-Pearson method) (14). Analyses will contain at least the descriptions listed in Table 5.2:

Table 5.2: Statistical analyses for safety observational objective

Safety Events	Time and Group	Description
Immediate unsolicited non-serious systemic AE	Within 30 minutes after vaccination(s) for all subjects in Groups 1 – 4	Percentage of subjects that have the event, MedDRA terms, intensity, relationship to vaccine, study discontinuation
Solicited injection site reactions	Within 7 days after vaccination(s) for all subjects in Groups 1 – 4	Percentage of subjects that have the event, onset, duration, intensity, action taken, study discontinuation, temperature collection routes
Solicited systemic reactions	Within 7 days after vaccination(s) for all subjects in Groups 1 – 4	Percentage of subjects that have the event, onset, duration, intensity, action taken, study discontinuation, temperature collection routes
Unsolicited non-serious AE/AR	Within 30 days after vaccination(s) for all subjects in Groups 1 – 4	Percentage of subjects that have the event, MedDRA terms, onset, duration, intensity, relationship, action taken, study discontinuation

AEs leading to study discontinuation	Within 30 days after vaccination(s) for all subjects in Groups 1 – 4 During the entire study period (ie, D0 to the 6-month follow-up telephone call on D180 [+14 days]) for all subjects in Groups 1 – 4	Percentage of subjects that have the event, MedDRA terms, time of onset, duration, intensity, relationship, action taken, study discontinuation
SAE (including AESI)	Within 7 days after vaccination(s) for all subjects in Groups 1 – 4 Within 30 days after vaccination(s) for all subjects in Groups 1 – 4 During 6-month follow-up after vaccine injection (ie, D31 to the 6-month follow-up telephone call on D180 [+14 days]) for all subjects in Groups 1 – 4 During the entire study period (ie, D0 to the 6-month follow-up telephone call on D180 [+14 days]) for all subjects in Groups 1 – 4	Percentage of subjects that have the event, MedDRA terms, onset, duration, relationship, seriousness criteria, outcome, study discontinuation
MAAE	Within 30 days after vaccination(s) for all subjects in Groups 1 – 4 (as unsolicited AE) D31 to 6-month follow-up telephone call, ie, D180 (+14 days) after vaccination(s) for all subjects in Groups 1 – 4	Percentage of subjects that have the event, MedDRA terms, onset, duration, relationship, seriousness criteria, outcome, study discontinuation

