3. Percentage of subjects with titer $\geq 1:8$ and $\geq 1:128$ and 95% CI
4. Percentage of subjects with titer ≥ 4 -fold rise from pre-vaccination to post-vaccination, and 95% CI
5. Percentage of subjects with rSBA vaccine seroresponse*

*rSBA vaccine seroresponse is defined as a post-vaccination titer $\geq 1:32$ for subjects with pre-vaccination rSBA titer $< 1:8$, or a post-vaccination titer ≥ 4 times the pre-vaccination titer for subjects with pre-vaccination rSBA titer $\geq 1:8$.

Data from subjects from MET50 (or MET43, if applicable) and MET59 will be combined and paired to evaluate antibody persistence and overall trends over 3-6 years post-priming with an MCV4 (ie, MenACYW conjugate vaccine-primed subjects or Menveo vaccine-primed subjects). If Menveo vaccine primed subjects that were not part of MET50 are recruited, those will not contribute to the assessment of antibody persistence.

Additional subgroup analyses of the hSBA vaccine seroresponse rates, hSBA titer $\geq 1:4$ and $\geq 1:8$, hSBA GMTs, rSBA vaccine seroresponse rates, rSBA titer $\geq 1:8$ and $\geq 1:128$, and rSBA GMTs will also be provided by number of years (3 years, 4 years, 5 years, and 6 years) elapsed since

priming vaccination received in either clinical studies MET50, MET43, or outside of Sanofi Pasteur trials, age group (13 to 17 years and 18 to 26 years), gender (Female and Male), and race (White, Asian, Black or African American, and Other).

Safety

Safety analysis will include but is not limited to the following:

1. The number and percentage of subjects reporting any solicited injection site reactions and solicited systemic reactions occurring from D0 to D07 after each vaccination will be summarized by study group for intensity, time of onset period, days of occurrence, and action taken. Since MenACYW conjugate vaccine and the concomitant MenB vaccines will be administered in different limbs, solicited injection site reactions can be distinguished between the two products, and will be analyzed and presented separately.
2. Immediate unsolicited systemic AEs and unsolicited AEs occurring up to D30 after each vaccination will be summarized.
3. The number and percentage of subjects reporting any unsolicited non-serious AEs will be summarized by study group, intensity, time of onset period, duration, and by MedDRA preferred term and system organ class (SOC), as well as by relationship to the study vaccine.

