Medical and scientific judgment should be exercised in deciding whether expedited reporting is appropriate in other situations, such as IMEs that may not be immediately life-threatening or result in death or hospitalization but may jeopardize the health of the subject or may require intervention to prevent one of the other outcomes listed in the definition above. These IMEs should also usually be considered serious. Examples of such events include allergic bronchospasm requiring intensive treatment in an emergency room or at home, blood dyscrasias or convulsions that do not result in inpatient hospitalization, or the development of drug dependency or drug abuse, new-onset diabetes, or autoimmune disease.

Adverse Reaction:

All noxious and unintended responses to a medicinal product related to any dose should be considered adverse reactions (AR).

(The phrase “responses to a medicinal product” means that a causal relationship between a medicinal product and an AE is at least a reasonable possibility).

The following additional definitions are used by Sanofi Pasteur:

Immediate Event/Reaction:

Immediate events are recorded to capture medically relevant unsolicited systemic AEs (including those related to the product administered) that occur within the first 30 minutes after vaccination.

Solicited Reaction:

A solicited reaction is an “expected” adverse reaction (sign or symptom) observed and reported under the conditions (nature and onset) prelisted in the protocol and CRB (eg, injection site pain or headache occurring between D0 and D07 post-vaccination).

By definition, solicited reactions are to be considered as being related to the product administered.

For injectable vaccines, solicited reactions can either be solicited injection site reactions or solicited systemic reactions.

^a The term “life-threatening” refers to an event in which the subject was at risk of death at the time of the event; it does not refer to an event which hypothetically might have caused death if it were more severe.

^b All medical events leading to hospitalizations will be recorded and reported as SAEs with the exception of: hospitalization planned before inclusion into the study or out-patient treatment with no hospitalization.

^c “Persistent or significant disability or incapacity” means that there is a substantial disruption of a person’s ability to carry out normal life functions.

The assessment of these reactions by the Investigator is mandatory.

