Unsolicited Adverse Event / Adverse Reaction:

An unsolicited AE is an observed AE that does not fulfill the conditions prelisted in the CRB in terms of diagnosis and / or onset window post-vaccination. For example, if headache between D0 and D07 is a solicited reaction (ie, prelisted in the protocol and CRB), then a headache starting on D07 is a solicited reaction, whereas, headache starting on D08 post-vaccination is an unsolicited AE. Unsolicited AEs includes both serious (SAEs) and non-serious unsolicited AEs.

Medically-Attended Adverse Event:

An MAAE is defined, for the purpose of this study, as a new onset of a condition that prompts the subject or subject's parent / guardian to seek unplanned medical advice at a health care provider's office or Emergency Department. This definition excludes pre-planned medical office visits for routine pediatric check-ups or follow-up visits of chronic conditions with an onset prior to entry in the study. Health care provider contact made over the telephone or by email will be considered a physician office visit for the purpose of MAAE collection. The outcome of the health care provider contact (whether it results in a prescription or not) will not be considered as a basis for reporting the event as an MAAE and all contacts should be reported. Sufficient data should be collected for the event to allow an assessment of the causality and diagnosis, if possible.

Injection Site Reaction:

An injection site reaction is an AR at and around the injection site. Injection site reactions are commonly inflammatory reactions. They are considered to be related to the product administered.

Systemic Adverse Event:

Systemic AEs are all AEs that are not injection or administration site reactions. Therefore, they include systemic manifestations such as headache, fever, as well as localized or topical manifestations that are not associated with the vaccination or administration site (eg, erythema that is localized but that is not occurring at the injection site).

Adverse Event of Special Interest:

An AESI is an event for which ongoing monitoring and rapid communication by the Investigator to the Sponsor must be done.

Such an event might warrant further investigation in order to characterize and understand it. Depending on the nature of the event, rapid communication by the study Sponsor to other parties (eg, regulators) might also be warranted.

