4.3.2.2 Safety Endpoints

The observational endpoints for the evaluation of safety are:

- 1) Occurrence, nature (Medical Dictionary for Regulatory Activities [MedDRA] preferred term), duration, intensity, and relationship to vaccination, and whether the event led to early termination from the study, of any unsolicited systemic AEs reported in the 30 minutes after vaccination(s)

- 2) Occurrence, time of onset, number of days of occurrence, intensity, action taken, and whether the reaction led to early termination from the study, of solicited (prelisted in the subject's diary card and CRB) injection site reactions occurring up to D07 after vaccination(s)
- 3) Occurrence, time of onset, number of days of occurrence, intensity, action taken, and whether the reaction led to early termination from the study, of solicited (prelisted in the subject's diary card and CRB) systemic reactions occurring up to D07 after vaccination(s)
- 4) Occurrence, nature (MedDRA preferred term), time of onset, duration, intensity, action taken, relationship to vaccination (for systemic AEs only), and whether the event led to early termination from the study, of unsolicited AEs up to D30 after vaccination(s)
- 5) Occurrence, nature (MedDRA preferred term), time of onset, duration, seriousness criteria, relationship to vaccination, outcome, and whether the event led to early termination from the study, of SAEs (including AESIs) after vaccination(s) from D0 through the end of the trial
- 6) Occurrence, nature (MedDRA preferred term), time of onset, duration, seriousness criteria, relationship to vaccination, outcome for MAAEs from D30 visit to the 6-month follow-up contact. MAAEs will be collected as unsolicited AEs up to the D30 (+ 14 days) visit

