4.4.2.3.2 Time of Onset

Time of onset will be computed using the same methodology than for unsolicited non-serious AEs described in Section 4.4.2.2.4.

SAEs (including AESIs) will be analyzed throughout the study using the following periods:

- Within 7 days after vaccination(s)
- Within 30 days after vaccination(s)
- During 6-month follow-up period: from D31 to the last telephone call on D180 (+ 14 days)
- During the entire study period: from D0 to the last telephone call on D180 (+ 14 days) (ie, all SAEs [including AESIs] occurred during the study)

An SAE (including AESI) with missing time of onset will be considered to have occurred just after the vaccination indicated by the visit number, so will be included in these tables.

Note: SAEs (including AESIs) that occurred before vaccination (negative time of onset) will not be included in analysis, but will be listed separately.

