5.3.1.1 Immediate

For unsolicited non-serious systemic AEs, a missing response to the “Immediate” field is assumed to have occurred after the 30-minute surveillance period and will not be imputed.

For SAEs, missing or partially missing elapsed time from last vaccination recorded if within 24 hours will be assumed to have occurred after the 30-minute surveillance period and will not be imputed. Such SAEs will not be considered as immediate.

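### The only 30-minute row in SAP Table 5.2 covers non-serious events alone, so the listed immediate-event analysis is narrower than safety endpoint 1

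*SAP*

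**What the plan says.** **Endpoint and definitions.** Safety endpoint 1 (protocol 9.3.2.2, SAP 4.3.2.2) takes any unsolicited systemic AE in the half hour after vaccination and sets no limit by seriousness. SAP 4.3.2.1 defines immediate events as "medically relevant unsolicited systemic AEs (including those related to the product administered) that occur within the first 30 minutes after vaccination". The same section says "Unsolicited AEs includes both serious (SAEs) and non-serious unsolicited AEs".

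**Analysis planned in the protocol.** Protocol 12.1.3, safety item 2: "Immediate unsolicited systemic AEs and unsolicited AEs occurring up to D30 after each vaccination will be summarized". Item 3 of that list, by contrast, is limited to non-serious unsolicited AEs.

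**Analysis listed in the SAP.** The one row of Table 5.2 (SAP 5.1.3.2) with a 30-minute window is "Immediate unsolicited non-serious systemic AE". For SAEs, SAP 4.4.2.3.2 states "SAEs (including AESIs) will be analyzed throughout the study using the following periods" and lists 7 days, 30 days, D31 to the D180 call, and the whole study. In Table 5.2 the shortest SAE window is "Within 7 days after vaccination(s) for all subjects in Groups 1 – 4".

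**Immediate SAEs.** SAP 5.3.1.1 deals with SAEs whose elapsed time since vaccination is missing or incomplete. They are taken to fall after the 30-minute observation: "Such SAEs will not be considered as immediate".

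**Declared changes.** SAP 5.7 names the added analysis set FAS3 and states that there was no other significant change outside a protocol amendment.

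**The concern.** The 30-minute observation is the trial's check for immediate reactions. Serious ones are foreseen: protocol 6.1.1.2 requires emergency equipment on site for anaphylactic and other immediate reactions, and the SAE definition gives an intensively treated allergic bronchospasm as an example of an event usually considered serious. If the only table for this window leaves out serious events, a zero in it does not mean that no immediate event occurred.

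A reader could easily take it that way. The protocol's own summary of MET50 (section 1.2.1.1) reports that there were no immediate hypersensitivity reactions. A similar sentence drawn from the Table 5.2 row in this study would rest on a count that a serious reaction cannot enter. The matter is most visible in the co-administration groups (100 subjects each), where a single event sets the percentage.

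**Working it through.** The plan states no figure for this point. The check compares texts, followed by a short illustration of size.

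**Step 1. Scope in each place.**

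| Place | Events in the 30-minute window |
|---|---|
| Endpoint 1 (protocol 9.3.2.2, SAP 4.3.2.2) | Any unsolicited systemic AE |
| Immediate event (SAP 4.3.2.1) | Unsolicited systemic AEs, no limit by seriousness |
| Unsolicited AE (SAP 4.3.2.1) | Serious and non-serious |
| Planned summary (protocol 12.1.3, item 2) | Unsolicited systemic AEs, no limit by seriousness |
| SAP Table 5.2, 30-minute row | Non-serious systemic AEs only |
| SAE periods (SAP 4.4.2.3.2, Table 5.2) | No 30-minute period |

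Protocol 12.1.3 uses the non-serious restriction in item 3 but not in item 2. The unrestricted wording for immediate events therefore reads as deliberate, and the limit first appears in the SAP.

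**Step 2. Where an SAE at 10 minutes is counted.** Of the four SAE periods, it enters three: 7 days, 30 days and entire study. It does not enter the D31 onward period or the 30-minute row.

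**Step 3. Whether those three rows can identify it as immediate.** SAP 4.4.2.3.2 takes its onset method from 4.4.2.2.4:

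onset = start date of event − date of last vaccination

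For an SAE at 10 minutes, and for one several hours later on the same date, the result is 0 days. The two cannot be told apart.

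**Step 4. Whether the information exists.** It does. SAP 4.3.2.3.3 lists elapsed time among the items recorded for an SAE, and 5.3.1.1 uses it. That section rules out only SAEs with missing or incomplete elapsed time. By implication an SAE with a recorded time within 30 minutes is immediate, but no listed output uses that status.

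**Step 5. Illustration of size.** Assume exactly one immediate SAE, no other immediate event, and denominators equal to the planned group sizes. Intervals are exact (Clopper-Pearson) 95%. With 0 events the upper limit is 1 − 0.025^(1/n). With 1 event the lower limit is 1 − 0.975^(1/n), and the upper limit is the 0.975 quantile of Beta(2, n − 1).

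| Denominator | Endpoint 1 as defined | Listed 30-minute row |
|---|---|---|
| Group 3 or 4, n = 100 | 1/100 = 1.0% (0.03 to 5.4%) | 0/100 = 0% (0 to 3.6%) |
| All subjects, n = 600 | 1/600 = 0.17% (0.004 to 0.93%) | 0/600 = 0% (0 to 0.61%) |

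The listed row counts a subset of the endpoint 1 events, so it can equal the endpoint percentage or fall below it, never exceed it.

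**The case against.** The strongest reply has four parts.

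- **Table 5.2 is a minimum.** SAP 5.1.3.2 first commits to describing the Section 4.3.2.2 results in all groups, and then presents the table as the least that will be produced. This stands. A reader might infer that serious immediate reactions are excluded from the endpoint; the documents do not support that. The endpoint is unrestricted, and what falls short is the analysis listed for it. But a minimum list only permits a further table and specifies none.

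- **Serious events are reported elsewhere.** A reader might also infer that an immediate SAE would vanish from the report, or appear only in the 7-day row. Neither is so. SAP 4.3.2.3.1 has it recorded and reported like any other SAE, and three SAE periods count it, with term, relationship, seriousness criteria and outcome. What those rows cannot convey is that it was immediate.

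- **Separating serious from non-serious events is consistent and labelled.** The SAP derives the two separately, and the 30-day row is also limited to non-serious events. This is a fair presentation choice. The 30-day row, however, has a matching 30-day SAE period, while the 30-minute row has no counterpart.

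- **Another output may fill the gap.** SAP 4.4.2.5.6 and 5.1.4 name a safety overview without giving its rows, and no table shells are in the documents. It may contain an immediate-SAE line. That cannot be settled here, so the point concerns what the SAP specifies, not what the final report will omit.

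**Conclusion.** The mismatch is real and minor. As specified, the immediate-event analysis leaves out serious events that endpoint 1 and protocol 12.1.3 include, no SAE period supplies them, and SAP 5.7 does not declare the narrowing. The listed percentage can therefore understate endpoint 1.

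The effect is confined to events classed as serious. An immediate allergic reaction or syncope that meets no seriousness criterion stays in the 30-minute row, so it would be wrong to say that immediate anaphylaxis as such is missed. Safety is an observational objective with no hypothesis tested, and the study's success criterion does not depend on this row. The 0% against 1.0% comparison in a group of 100 rests on one hypothetical event, and the 0% applies to a row labelled non-serious. The documents give no expected rate of immediate SAEs.

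**What to change.** Either of two changes closes the gap.

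1. In Table 5.2, relabel the row *Immediate unsolicited systemic AE (serious and non-serious)* and show serious events as a sub-row. This is preferable because it gives one percentage that matches endpoint 1.
2. Add *Within 30 minutes* to the SAE periods in SAP 4.4.2.3.2 and to the SAE row of Table 5.2. The endpoint 1 percentage should then still be stated, because a subject with both kinds of event would be counted twice if the two rows were added.

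In both cases, classify SAEs by recorded elapsed time and keep the missing-time rule in 5.3.1.1. If the restriction to non-serious events was intended, record it in SAP 5.7 with the reason.

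The cost is a change of SAP wording and one table shell. No new data are needed.
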